#### Statistical methods

This is the pivotal Phase III study with PQ Grass. The primary endpoint of the study will be the CSMS averaged over the peak GPS.

The difference in CSMS between PQ Grass and placebo will be evaluated using a linear mixed model. Subjects with missing daily CSMS during the peak GPS will be included in the primary analysis by using multiple imputation methods to impute missing values on a by-day level.

The statistical analysis will be performed using a linear mixed model. In the context of the adaptive design, a 1-sided testing will be used using group sequential Pocock boundaries chosen such that an overall 1 sided type 1 error rate of 2.5% was preserved.

For the interim analysis after Year 1, the 1-sided p-value was therefore to be compared with  $\alpha$  = 0.01419 for a statistically significant superiority of the active treatment over placebo.

The difference between PQ Grass and placebo will be estimated using least squares (LS) means. Two-sided appropriate confidence intervals (CIs) for the difference between treatment groups

[figure not shown]

will be provided. The difference between treatment groups will also be presented in percent relative to the LS mean in the placebo group.

The secondary endpoints will generally be analyzed using a similar statistical approach as the primary endpoint. The statistical hypotheses for the key secondary endpoints will only to be tested in a confirmatory sense if the analysis of the primary endpoint is statistically significant. Multiplicity in the key secondary endpoints will be addressed.

The frequency, relationship and severity of AEs and frequency of premature discontinuations from treatment or study due to AEs will be assessed within each treatment group.

**Adjudication Committee:** Yes **Trial Oversight Committee:** Yes

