## 6.2 Handling of withdrawals (drop-outs), missing values and outliers

Discontinued or withdrawn subjects will not be replaced if they withdrew due to AE. Subjects withdrawn early from the clinical trial due to other reasons may be replaced. Data collected for subjects whose participation is terminated is evaluated with all data as collected until withdrawal and during a possible follow-up for safety. Missing data for the primary variable on a by-day level will be handled using multiple imputation methods. Similarly, missing data in covariates included in the analysis model of CSMS will be imputed to allow the inclusion of all subjects from the FAS into the primary analysis.

ncomplete dates will be imputed temporarily for the categorisation of AEs or concomitant medications. The corresponding strategies are described in the corresponding sections.

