#### 7.7.1.5. Statistical analysis method

The primary efficacy analysis for this clinical trial will be a comparison of the mean average CSMS during the peak GPS in the PQ Grass versus the placebo group.

The following null and alternative hypotheses will be tested for the primary endpoint, based on all subjects who received at least 1 injection of the clinical trial medication, i.e., are included in the FAS (two-sided test):

μ: arithmetic mean of the average CSMS over the peak GPS

The primary efficacy endpoint will be evaluated using a linear mixed model.

The difference between PQ Grass and placebo will be estimated using least squares (LS) means. Two-sided 95% repeated confidence intervals (RCIs) for the difference between treatment groups will be provided at the interim and (if applicable) at the final analysis, which will ensure 95% probability despite calculation at the interim and (if applicable) final analysis.

The difference between treatment groups will also be presented in percent relative to the LS mean in the placebo group, and the CI will be calculated by approximating the SE using the delta method.

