#### 7.7.2.5. Serum grass-specific IgG4 at Visit 7 compared to baseline

Blood samples are collected at screening, Visit 7 and Visit 10 for the evaluation of several immunoglobulin parameters, including grass-specific IgG4 [mg/L].

Summary statistics will be created by visit and treatment group for the absolute values (Baseline, Visit 7 and Visit 10) and the absolute change from baseline (to Visit 7 and Visit 10).

The change from baseline to Visit 7 in grass-specific IgG4 [mg/L] will be additionally analysed using the same linear mixed model as specified in the primary analysis with the baseline value as additional covariate.

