## 7.7.2.6. Standardised Rhinoconjunctivitis Quality of Life Questionnaire (RQLQ[S]) averaged over the peak GPS

## 7.7.2.6.1. Standardised rhinoconjunctivitis Quality of life questionnaire

Rhinoconjunctivitis quality of life will be assessed using the RQLQ(S). The RQLQ(S) is a questionnaire which consists of 28 questions in 7 domains (activity limitation, sleep problems, nose symptoms, eye symptoms, non-nose/eye symptoms, practical problems, and emotional function). Each question is scored on a scale from 0 to 6 (0 = not impaired at all to 6 = severely impaired). Subjects will be issued the RQLQ questionnaire at Visits 2, 9 and 10. The Visit 2 RQLQ will be the baseline RQLQ.

The total score defined as the mean of all 28 responses will be aggregated as an outcome variable on a subject level by taking the mean of the scores from Visits 9 and 10 that can be attributed to the peak GPS.

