## 7.7.2.6.2. RQLQ[S] averaged over the peak GPS

The average total RQLQ score during the peak GPS will be calculated if at least one score at Visit 9 or 10 is reported during the peak GPS. It will be considered missing if the RQLQ questionnaire has not been filled at any of these visits or both visits do not fall within the peak GPS. Missing values of the RQLQ score will not be imputed.

The total RQLQ score and its change from baseline (Visit 2) will be summarised by visit and treatment group for the FAS. In addition, summary statistics will be created for the RQLQ during the peak GPS and its change from baseline.

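### The public SAP text states no Visit 2 baseline term for the RQLQ(S) comparison, although it adds one for IgG4; adding it would be a nearly free precision gain

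*SAP*

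**What the plan says.** SAP 7.7.2.6.1 schedules the questionnaire at Visits 2, 9 and 10 and fixes the reference value: "The Visit 2 RQLQ will be the baseline RQLQ". The outcome is an in-season level, formed by "taking the mean of the scores from Visits 9 and 10 that can be attributed to the peak GPS".

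SAP 7.7.2.6.2 then gives the baseline two uses, both descriptive. By visit: "The total RQLQ score and its change from baseline (Visit 2) will be summarised by visit and treatment group for the FAS". For the peak season: "In addition, summary statistics will be created for the RQLQ during the peak GPS and its change from baseline". The same section says that missing RQLQ scores are not imputed. It shows no hypothesis, model or covariate list for the between-arm comparison.

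The only model rule that reaches RQLQ(S) is in the protocol, Statistical methods: "The secondary endpoints will generally be analyzed using a similar statistical approach as the primary endpoint". For the primary endpoint, SAP 7.7.1.5 says: "The primary efficacy endpoint will be evaluated using a linear mixed model". The terms of that model are not listed in the public text, although SAP 6.2 shows that it has covariates: "missing data in covariates included in the analysis model of CSMS will be imputed".

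For IgG4, SAP 7.7.2.5 is explicit. The change to Visit 7 is analysed "using the same linear mixed model as specified in the primary analysis with the baseline value as additional covariate".

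**The concern.** RQLQ(S) is tested for confirmation. SAP 7.7.2 spreads a two-sided 5.0% over 8 key secondary endpoints by the Fallback method, and the listed endpoints count to 8 with RQLQ(S) among them. Some people score their quality of life worse than others whatever the season. A pre-treatment score on the same instrument can remove part of that between-subject variance, together with any chance imbalance between the arms.

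The trial already collects that score, but nothing in the public text puts it into the model. What is at stake is the width of the confidence interval and the power for one alpha-bearing secondary endpoint. It also matters that the covariate choice is fixed before unblinding. Validity is not at stake: in a randomised comparison, leaving the covariate out causes no bias and does not raise the type I error.

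**Working it through.** **Does the default rule bring in the baseline?** The protocol's Schedule of activities starts eDiary recording at Visit 8, after the injections at Visits 2 to 7. No pre-treatment CSMS is therefore scheduled, and a model carried over from CSMS has no reason to hold a pre-treatment value of its own outcome. The wording for IgG4 fits this: it takes the primary model and adds the baseline. Of the 8 key secondary endpoints, six come from the diary: CSMS over the entire season, dSS peak and entire, dMS peak and entire, and well days. They have no scheduled baseline. IgG4 and RQLQ(S) do, and only the IgG4 text puts it in the model.

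**Does the IgG4 wording carry over from a change to a level?** Yes. Write Y for the outcome, B for the baseline and T for treatment. If Y − B = a + τT + cB, then Y = a + τT + (c + 1)B. The treatment effect τ is the same, so the same sentence serves both endpoints.

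**Size of the gain.** The documents give no RQLQ(S) effect size, SD, power or correlation, so there is no planned figure to reproduce.

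Inputs:
- N = 555 randomised in Year 1 (protocol, Number of subjects planned). The RQLQ(S) analysis can be smaller, because missing scores are not imputed and a visit must fall in the peak season.
- r = correlation between the Visit 2 and average peak-season scores: an assumption, shown from 0.1 to 0.5.
- Alpha: two-sided 5%, or 5%/8 = 0.625% if the Fallback alpha is split equally. The split is not shown, so equality is an assumption.
- Unadjusted power of 80%: an assumption, for illustration only.

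Formulas:
- variance ratio, adjusted to unadjusted = 1 − r²
- SE ratio = √(1 − r²)
- unadjusted N that gives the same precision = 555/(1 − r²)
- adjusted power = Φ[(z(1−α/2) + z(0.80))/√(1 − r²) − z(1−α/2)]

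| r | Variance ratio | SE ratio | Equivalent N | Power at 5% | Power at 0.625% |
|---|---|---|---|---|---|
| 0.1 | 0.99 | 0.995 | 561 | 80.4% | 80.5% |
| 0.2 | 0.96 | 0.980 | 578 | 81.6% | 82.0% |
| 0.3 | 0.91 | 0.954 | 610 | 83.6% | 84.5% |
| 0.4 | 0.84 | 0.917 | 661 | 86.4% | 87.8% |
| 0.5 | 0.75 | 0.866 | 740 | 89.9% | 91.8% |

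Example at r = 0.3: 1 − 0.09 = 0.91, and 555/0.91 = 610. At 5%, (1.960 + 0.842)/0.954 − 1.960 = 0.977, and Φ(0.977) = 83.6%.

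Two points limit these figures. Visit 2 comes before a treatment course of about 16 weeks that ends before the season (protocol, Overall Design), so it is an out-of-season score and r may be low. And if the model already holds covariates, the r that counts is the partial correlation given those terms, which may be smaller.

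**The case against.** The strongest objection is that silence is not exclusion. The public SAP is abridged: its numbering skips 7.7.1.3, 7.7.2.1 and 7.7.2.4.1, and no RQLQ(S) model is shown at all. A reader might infer that the plan leaves the baseline out of the RQLQ(S) test and so gives up precision. The documents do not support that. They show only that no baseline term is stated, and the protocol's general rule is loose enough to allow one. This part of the objection stands, which is why the request includes the option simply to confirm.

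It can also be said that the IgG4 endpoint is defined against baseline while RQLQ(S) is a level, so treating the two differently is not a contradiction. That is correct. The IgG4 section serves as ready-made wording and does not prove an inconsistency.

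A reader might further infer that the plan will test change from baseline, which can be noisier than the in-season score when r is low. SAP 7.7.2.6 does not say so. It defines the outcome as the in-season mean and confines change to summaries, so there is no criticism to make there.

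Last, a missing Visit 2 score is not dealt with for this endpoint. The covariate imputation in SAP 6.2 is stated for the CSMS model only, and 7.7.2.6.2 rules out imputing RQLQ scores without saying whether that includes the baseline. Without a rule, adjustment could drop subjects. This stands, and the fix has to cover it.

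**Conclusion.** The point holds as a precision improvement with a request for clarification. In the public text, the Visit 2 RQLQ(S) score appears only in descriptive summaries, and the confirmatory comparison has no stated baseline term. Under assumed r of 0.1 to 0.5, adding the term lowers the variance by 1% to 25%. That equals 561 to 740 unadjusted subjects in place of 555, and less if existing covariates explain part of the same variance. For an out-of-season baseline, the lower end of that range is quite possible. The cost is about one degree of freedom. An unadjusted analysis would remain valid, and neither the primary endpoint nor the type I error is affected.

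**What to change.** Before unblinding, add to SAP 7.7.2.6:

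- The confirmatory comparison of the average peak-season RQLQ(S) uses the primary linear mixed model with the Visit 2 RQLQ(S) total score as an additional covariate. If a paragraph outside the public text already says this, confirm it.
- A subject with a missing Visit 2 score stays in the analysis, under a named rule such as imputation of the covariate only.
- The no-imputation rule in 7.7.2.6.2 applies to the outcome scores at Visits 9 and 10 and not to the baseline covariate.

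Change from baseline can stay as a descriptive summary. The cost is two or three sentences and a small programming step for missing baselines. No new data are needed.

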## 7.8 Safety

Analysis of all safety and tolerability variables including solicited pre-specified local and systemic reactions will be based on the SAF. Summary statistics will be provided for safety variables. Alert ranges will be defined for laboratory values lying outside the normal range to a clinically relevant degree. Any measurement fulfilling these criteria will be presented in subject listings.

## 7.8.1 Investigational drug/placebo exposure and compliance

The number and percentage of subjects having received treatment will be summarised per treatment group and treatment visit (scheduled injections as well as unscheduled injections for dose repeat and dose reduction ) for the FAS (randomised treatment) and the SAF (actual treatment).

The actually received cumulative dose in SU is calculated based on the actually received kit and vial numbers entered in the eCRF. The planned cumulative dose is based on the randomised treatment (27600 SU for the PQ Grass treatment group).

Summary statistics will be provided for the number of injections received, the actually received cumulative dose in SU and the ratio of the cumulative dose actually received and planned [%]. This ratio can only be calculated for the PQ Grass treatment group and the corresponding planned cumulative dose is 27600 SU for every subject. Please note that ratios greater than 100% might result for subjects receiving additional unscheduled injections. This summary will be provided for the FAS (randomised treatment) and the SAF (actual treatment).

Any subject with dose modifications or unscheduled injections will be listed in a separate listing providing all details on all injections received.

For this clinical trial, any dose of investigational drug/placebo greater than the dose prescribed (for each of the dosing visits) within the clinical trial protocol represents an overdose. A separate listing will be generated including only subjects that experienced an overdose.

#### 7.8.2 Adverse events

All Adverse events during the course of the study will be coded using the medical dictionary of regulatory activities (MedDRA) current at the start of the study and summarised by treatment group. AEs will be summarised by treatment, primary system organ class (SOC), preferred term (PT), relationship assessment and severity.

All solicited AEs identified via separate phone calls for the US will also be entered in the general AE section of the eCRF. Therefore, no separate analysis will be conducted.

The SOCs as well as the PTs within each summary table will be sorted by frequency in the total column in decreasing order.

AEs will be reported separately as pre-treatment or screening period AEs (any AE occurring prior to the first injection of study medication) and treatment emergent AEs (any AEs after first injection of study medication).

In general, all adverse events will be listed by treatment group, subject number, and period. For AE onset and end dates, the study day relative to the first injection will be listed.

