### **Objectives and Endpoints:**

Objectives	Endpoints						
Primary Efficacy							
To evaluate the efficacy of PQ Grass 27600 SU in subjects with grass pollen induced SAR and/or rhinoconjunctivitis based on symptoms and medications.							
Secondary Efficacy							
To evaluate the treatment effect of PQ Grass on the CSMS over the entire GPS.	CSMS averaged over the entire (or truncated) GPS.						
To evaluate the quality of life.	RQLQ(S) measured within the peak GPS.						
To evaluate the effect of PQ Grass 27600 SU on IgG4.	• Serum grass specific IgG4 at Visit 7 compared to baseline.						
To evaluate the treatment effect of PQ Grass on the dSS and dMS components of the CSMS over the GPS.	
 
dSS component of the CSMS averaged over the peak GPS and entire (or truncated) GPS.
 
dMS component of the CSMS averaged over the peak GPS and entire (or truncated) GPS.
 
						
To evaluate the potential of PQ Grass 27600 SU to reduce symptom burden and the need for medication use.	The number of well days during the peak GPS.						
Safety							
To evaluate the safety and tolerability of PQ Grass in subjects with grass pollen induced SAR and/or rhinoconjunctivitis.	
 
Frequency, severity and relationship of AEs to treatment.
 
Frequency of AEs leading to premature discontinuation from treatment or clinical trial.
 
						
	
 
Frequency of AESI.
 
Changes in clinical laboratory values (serum chemistry, haematology and urinalysis) between screening and Visit 11.
 
Changes in vital signs at all treatment visits.
 
						

**Abbreviation s**AE = adverse event; AESI = adverse event of special interest; CSMS = combined symptom and medication score; dMS = daily medication score; dSS = daily symptom score; GPS = grass pollen season; Ig = immunoglobulin; RQLQ(S) = Rhinoconjunctivitis Quality of Life Questionnaire with standardised activities; SAR = seasonal allergic rhinitis; SU = standardised units;

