# Subjects screened, randomised, treated, completed and discontinued prematurely

Subjects are defined as completing the clinical trial, including the safety follow-up, if the item "Premature study termination" is ticked as "No" on the "End of study evaluation" page.

Subjects are defined as prematurely discontinuing the clinical trial if this item is marked as "Yes".

Subjects are defined as completing treatment, if the item "Premature treatment termination" is ticked as "No" on the "End of treatment" page. Subjects are defined as prematurely discontinuing treatment if this item is marked as "Yes".

A summary table will be created including:

- the number of screenings (including re-screenings),
- the number of subjects who were screened (i.e., signed the informed consent),
- the number of screen failures,
- the number of subjects who were randomised,
- the number of subjects who were treated,
- the number and percentage of subjects who completed treatment,
- the number and percentage of subjects who prematurely discontinued treatment,
- the number and percentage of subjects who completed the clinical trial including safety follow-up, and
- the number and percentage of subjects who prematurely discontinued the clinical trial.

This analysis will be repeated by for Europe and United States separately, by pooled geographical region (if applicable), and geographical region used for randomisation.

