## 7.8.2 Summary tables for analysis of adverse events

The number and percentage of subjects with

- TEAEs
- ADRs
- treatment emergent serious adverse events (SAEs)
- serious ADRs
- treatment emergent adverse events of special interest (AESIs)
- TEAEs leading to premature discontinuation of treatment
- ADRs leading to premature discontinuation of treatment
- TEAEs leading to temporary discontinuation of treatment
- ADRs leading to temporary discontinuation of treatment
- TEAEs leading to premature discontinuation of study

- ADRs leading to premature discontinuation of study
- local AEs
- systemic AEs
- other AEs, not classified as local or systemic AEs

will be summarised by treatment group, MedDRA SOC and PT.

For the analysis of the severity and the relationship of AEs, the worst severity and the strongest relationship per subject and type of AE will be used. The number and percentage of subjects with at least one AE by MedDRA SOC, PT and severity/relationship will be displayed only for

- all TEAEs
- all ADRs

all serious adverse events (SAEs).

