## 7.8.2.2 Overview summary tables for adverse events

An overview summary of the following AE types will be provided, presenting number and percentage of subjects experiencing at least one AE of the respective AE type in each treatment group as well as the corresponding number of events.

- Any AE
- Any ADR
- Any severe AE
- Any severe ADR
- Any AE of special interest
- Any serious AE
- Any serious ADR
- Any non-serious AE
- Any AE leading to premature discontinuation from treatment
- Any AE leading to temporary discontinuation from treatment
- Any ADR leading to premature discontinuation from treatment
- Any ADR leading to temporary discontinuation from treatment
- Any AE leading to premature discontinuation of study
- Any ADR leading to premature discontinuation of study
- Any local TEAE
- Any systemic TEAE
- Any other TEAE, not classified as local or systemic AE

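### Does folding the US phone-solicited adverse events into the general AE tables, with no split by region, make the reported AE frequencies unreliable?

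*SAP*

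**What the plan says.** SAP 7.8.2 (Adverse events) mentions a collection route specific to the US: "All solicited AEs identified via separate phone calls for the US will also be entered in the general AE section of the eCRF". It draws the consequence at once: "Therefore, no separate analysis will be conducted".

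The AE tables that follow "will be summarised by treatment group, MedDRA SOC and PT", with a further breakdown by severity and relationship for some AE types. Local, systemic and other AEs are separate lines there. The overview in SAP 7.8.2.2 is built the same way, "presenting number and percentage of subjects experiencing at least one AE of the respective AE type in each treatment group". Individual events remain available: "In general, all adverse events will be listed by treatment group, subject number, and period".

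SAP 7.8 (Safety) says that the analysis of safety variables, "including solicited pre-specified local and systemic reactions", uses the Safety Set. It does not restrict the solicited reactions to one region.

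Region does appear elsewhere. For the disposition summary, SAP 7.2 says "This analysis will be repeated by for Europe and United States separately", and it also refers to a geographical region used for randomisation. Among the safety endpoints, the protocol's Objectives and Endpoints table lists "Frequency, severity and relationship of AEs to treatment".

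**The concern.** Active prompting usually brings in more mild reactions than spontaneous reporting does. The SAP mentions separate calls only for the US, and the protocol's Schedule of activities shows only the two follow-up calls, at 12 and 24 weeks after the last injection, that every subject receives. A reader could conclude that US subjects are prompted and European subjects are not.

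If so, a pooled AE percentage would be a weighted average of two differently measured rates, with the US share as the weight. For an injected product the local and systemic reactions would be affected most, and AE frequency is a named safety endpoint. Without a regional table, a real regional difference and a difference in ascertainment could not be told apart. The SAP's own argument seems not to meet this: entering the events in the general section ensures that they are counted, not that they were collected alike. Since disposition is already repeated by region, leaving AEs unsplit looks like an oversight.

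**Working it through.** The documents give no AE rate, no capture rate and no US share of subjects, so there is no planned figure to reproduce. The check has three parts.

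**1. Does the text show different collection?** The concern needs Europe to be solicited less than the US. SAP 7.8.2 says that separate US calls exist; it says nothing about how European subjects are asked. SAP 7.8 speaks of solicited, pre-specified reactions for the whole Safety Set. The two sections fit together if reactions are solicited throughout and the US adds a telephone route. They also fit if Europe is solicited less. The text does not decide between these readings, so the premise is possible but not shown.

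**2. What would follow if collection did differ?** All inputs here are assumptions: true local reaction rate 70% on active and 25% on placebo; 95% captured when solicited; European capture *u*; US share *w*; capture within a region equal in both arms.

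Recorded pooled rate = true rate × [*w* × 0.95 + (1 − *w*) × *u*].

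The bracket at *w* = 0.3 and *w* = 0.7:
- *u* = 0.60: 0.285 + 0.420 = 0.705, and 0.665 + 0.180 = 0.845
- *u* = 0.80: 0.285 + 0.560 = 0.845, and 0.665 + 0.240 = 0.905
- *u* = 0.95: 0.950 at both

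| European capture *u* | Active rate (0.70 × bracket), *w* 0.3 → 0.7 | Shift | Risk difference (0.45 × bracket) | Risk ratio |
|---|---|---|---|---|
| 0.60 | 49.4% → 59.2% | 9.8 points | 31.7 → 38.0 points | 2.8 |
| 0.80 | 59.2% → 63.4% | 4.2 points | 38.0 → 40.7 points | 2.8 |
| 0.95 | 66.5% → 66.5% | 0 | 42.8 → 42.8 points | 2.8 |

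The last row is equal solicitation, where the mix has no effect. The constant risk ratio (0.70/0.25) follows from equal capture in the two arms.

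A second assumed pattern drops the common capture factor: recorded rates of 60% and 30% (active, placebo) in the US, 45% and 20% in Europe. At *w* = 0.3 the arms are 49.5% and 23.0%, a difference of 26.5 points. At *w* = 0.7 they are 55.5% and 27.0%, a difference of 28.5 points. The active rate moves by 6 points and the contrast by 2.

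These shifts compare different hypothetical trials. This trial will have one realised mix, and its pooled percentage will correctly describe the AEs recorded in its own subjects.

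**3. What would a regional table add?** Take the 555 Year 1 subjects and assume half are in the US: 555/2 × 0.5 ≈ 139 per region and arm.
- 95% half-width for one regional rate: 1.96 × √(0.665 × 0.335/139) ≈ 8 points.
- 95% half-width for a US–Europe difference within the active arm, 66.5% against 42% or 56%: 1.96 × √[(0.665 × 0.335 + 0.42 × 0.58)/139] ≈ 11.4 points, and likewise 11.4 with 0.56 × 0.44.

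The gap is 0.70 × (0.95 − 0.60) = 24.5 points in the first case, which would show clearly, and 0.70 × (0.95 − 0.80) = 10.5 points in the second, which would not. Neither result would identify the cause, because pollen exposure, practice and population also differ between regions.

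**The case for a change.** The strongest case for the concern is that the SAP's reasoning has a gap. Counting the US events in the general section does not make collection comparable, the text supplied describes no European counterpart to the calls, and a split that exists for disposition could be repeated for AEs at little cost. The arithmetic also shows that, under unequal capture, the absolute rate and the risk difference depend on the mix even though the risk ratio need not.

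Part of this stands. The AE sections supplied contain no regional table, and the documents do not say how reactions are solicited in Europe. But the public protocol is a synopsis and the SAP is abridged, so silence about Europe is not evidence that Europe is unsolicited. Nor does pooling remove information: all events are in the AE data, local and systemic reactions have their own lines, and a regional count can be made later from the same locked data. Unequal capture would lower the recorded frequencies, but blinding and 1:1 allocation keep the comparison of recorded events between arms fair.

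**Conclusion.** The concern does not hold. Followed as written, the plan counts every solicited US event, shows local and systemic reactions separately by arm, and leaves the comparison between arms valid. Safety is summarised descriptively in the text supplied; no hypothesis test or decision rule there rests on an absolute AE rate, so the lack of a regional split changes no result and no error rate.

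The size is zero if Europe is solicited as the US is. Under the assumed unequal capture it is 4.2 to 9.8 points in the active-arm rate between hypothetical trials with 30% and 70% US subjects, which is not an error in this trial's reported rate. The conclusion rests on two things: no passage shows weaker solicitation in Europe, and capture within a region is alike in both arms, which the double blind is meant to secure. A document showing that European subjects were not asked about reactions would affect how the absolute rates are read, but not the comparison between arms.
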